2.2. Appointment Not Found

Check if the appointment is not listed above.

Protocol Feasibility

School of Medicine and Public Health [policy 70.10](#) requires departments to assess and document the feasibility of non exempt human subjects research prior to IRB review.

SMPH departments are required to evaluate and confirm local capacity (e.g., qualified staff, adequate resources and facilities, sufficient patient

population) to warrant pursuit of a research study. Feasibility assessments help identify and address potential factors that can prevent or slow study execution.

Please see <https://ictr.wisc.edu/protocol-feasibility/> for guidance and to download the "Research Feasibility Attestation Form."

1. Research Feasibility Attestation Form

Upload the signed "Research Feasibility Attestation Form."

There are no items to display

Study Team

1. Points of Contact Selection

Points of contact can edit the application and will receive email notifications about this submission.

Please do not use personal email addresses (e.g., Gmail, Hotmail, etc.). A campus business email can be changed following the instructions [here](#).

If the PI is serving as the only study point of contact, indicate that here.

Can't find someone in the chooser? See [this FAQ](#) for help.

To register a NetID, [click here](#).

1.1. Funding Sources

For **federal funds**, pending sources may be listed if the grant has received a highly meritorious score. For example, an impact score of <30 is an indication of a highly meritorious NIH grant proposal. Receipt of a request for Just In Time (JIT) documentation is another indication of a highly meritorious proposal.

For **non-federal funds**, pending sources may be listed if you have confirmation from the sponsor that funding will be awarded due to merit AND the sponsor has a peer-review process.

For **industry**, do not select industry sponsors who are only providing drug/device OR only limited support for the study.

* Use this chooser to select each funding source administered through UW-Madison that will support this study or project.

Funding Source Details

PI Name	[name]
Proposal ID	MSN245065
Award ID	MSN245065
Funding Title	mHealth to Enable Task Sharing for Hypertension Care in LMIC
Project ID	No Value Entered
Sponsor (Source)	DHHS, PHS, NATIONAL INSTITUTES OF HEALTH
Sponsor Reference Number	1R21TW011891-01
Primary Sponsor	No Value Entered
Primary Sponsor Reference Number	No Value Entered
Federal	Yes
Status	Active
Start Date	8/10/2021
End Date	4/30/2026

2. Other Funding

* Do you have pending or approved funding NOT listed on this page?

Yes No

Conflict Of Interest

Please review the study team member Outside Activities Report (OAR) and managed entities data below before answering the questions on this page.

The following study team members have not completed their OAR for the year:

[name], [name], [name], [name], [name], [name], [name]

NOTE: Per campus policy all study team members must submit an OAR every year and keep it up to date.

No study team members have any managed entities at this time.

1. Intellectual Property

* Do any study team members involved in the design or conduct of the research (including their spouses and dependent children) own intellectual property that will be used in the study or project?

Yes No

2. Other Entities

* Besides the sponsor(s) of this project or entities listed above, do any study team members have a fiduciary or financial relationship with entities that will be involved in this study or that may be significantly affected by it?

Yes No

3. Incentives

* Do any of the study team receive any incentives for recruiting human subjects or any other purpose directly related to the study or project?

Yes No

VA Status

All studies that fall under Madison VA purview must be reviewed and approved by the VA Research and Development (R&D) Committee in addition to being reviewed by the Health Sciences IRB. For information about the VA R&D Committee review process, please contact [contact].

1. VA Status

* Does this study involve the Madison VA (Wm. S. Middleton VA Hospital); e.g., funding from the VA, conducted under VA appointment, use of VA facility, recruitment of veterans or use of their data or samples at the Madison VA?

Yes No

Scientific Review: PRMC & CRU

1. Cancer Related

* Is the scientific question of the protocol cancer related?

Yes No

2. Targeting Cancer Patients

* Are you specifically targeting cancer patients for enrollment in this study?

Yes No

3. Use of Cancer Data or Images

* Does this study involve the review and/or use of biological specimens/data/images/records from cancer patients?

Yes No

4. Use of CRU

If the answer to this question is Yes, you must upload a copy of the CRU application to the Submit activity form.

* Will this study use the Clinical Research Unit (CRU)?

Yes No

ClinicalTrials.gov Information

This page is designed to aid in identifying ClinicalTrials.gov registration requirements. Registration may be required by the FDA, NIH, or if you are planning to publish in a journal that follows International Committee of Medical Journal Editors (ICMJE) guidance. Please answer each question carefully.

UW-Madison has a free service available to assist you in registering your record with ClinicalTrials.gov. Contact [contact] for more information.

For information on registration and results reporting requirements see our [KnowledgeBase page](#) or contact the Office of Research Compliance at [contact].

1. Study Intervention(s)

Prospective assignment means enrolling study subjects and collecting data on them in the future. It is a study not solely reliant on existing or retrospective data. It is not a requirement to have multiple groups or arms for a study to be considered prospectively assigned.

An **intervention** is any manipulation of the subject or subject's environment for the purpose of modifying one or more health-related biomedical or behavioral processes and/or endpoints. Any study that is not observational (where participants may receive a drug, device, medical procedure, or behavioral intervention as part of their standard clinical care) should be considered interventional. Examples include: drugs/small molecules/compounds; biologics; devices; procedures (e.g., surgical techniques); delivery systems (e.g., telemedicine, face-to-face interviews); strategies to change health-related behavior (e.g., diet, cognitive therapy, exercise, development of new habits); treatment strategies; prevention strategies; and, diagnostic strategies.

A **health-related biomedical or behavioral outcome** is defined as the pre-specified goal(s) or condition(s) that reflect the effect of one or more interventions on human subjects' biomedical status, behavioral status, or quality of life. Examples include: positive or negative changes to physiological or biological parameters (e.g., improvement of lung capacity, gene expression); positive or negative changes to psychological or neurodevelopmental parameters (e.g., mood management intervention for smokers; reading comprehension and /or information retention); positive or negative changes to disease processes; positive or negative changes to health-related behaviors; and, positive or negative changes to quality of life.

* Are subjects prospectively assigned by the protocol to any intervention(s) that are being evaluated for any health-related biomedical or behavioral outcomes?

Yes No

2. ClinicalTrials.gov Determinants

* Check the box(es) that apply to this study:

NIH funded, when registration is a required condition of the grant (consult your award letter or with your NIH Program Officer if unsure)

3. FDA or NIH Requirement

* Based on your responses, registration with ClinicalTrials.gov may be required by the FDA or NIH. Will UW-Madison (study team or service line support staff) register the study with ClinicalTrials.gov?

Yes No

External Collaborations

1. Outside UW Activities

* Will any UW/UW Health or Madison VA personnel conduct any of the following study activities at locations outside the UW/UW Health or Madison VA: subject recruitment, obtaining informed consent, or interacting or intervening with subjects?

Yes No

1.1. Describe Activities at Non-UW Locations

* Describe what activities will be occurring outside the UW/UW Health or Madison VA and at which locations.

Recruitment of subjects and all study activities will occur in the rural communities of the municipality of San Lucas Tolimán at mobile clinics run by our Guatemalan partner, the San Lucas Mission (SLM).

2. Requesting UW Serve as IRB

Please note that you must consult with RELIANT before you submit a request for the UW to serve as the reviewing IRB for external sites or individuals. A consultation may be requested [here](#).

* Are you requesting that UW Madison serve as the reviewing IRB for any external sites or individuals?

Yes No

Guatemalan study team members will access subject data through the secure, HIPAA-compliant CommCare platform. The CommCare application itself is encrypted and password-protected and will only be accessed on password-protected Android devices and Windows computers, which will be kept in a locked cabinet or room when not in use.

9. Return of Data or Specimens

* Address whether the data, images or specimens will be returned to UW Madison and if not, why not (e.g., samples will be exhausted).

Data will be shared with study personnel at UW Madison through the CommCare platform, but will also be retained with San Lucas Mission staff for purposes of ongoing patient care.

10. Informing Subjects

* Are subjects being informed of the plans to share data, images, or specimens?

Yes No

Study Procedures and Special Populations

1. Study Procedures Involved

Select "Review or use of information from health care records"

* If your study involves any of the following special procedures or considerations, additional information may be needed. Select all that apply. If none apply, check Not Applicable.

Interviews, focus groups, surveys, questionnaires, assessments (e.g., QOL, SCID, BDI, etc.)

International Research

2. Special Populations

If you will collect data points identifying individuals as any of the following, select the corresponding box(es).

* Is the research designed to include any of the following populations? Select "Not Applicable" if the research will not include any of the populations below. NOTE: If enrolling pregnant women, children, or prisoners, and you can identify them as such, check the box.

Illiterate or Low-literacy participants

Non-English Speaking subjects or subjects whose primary language is not English

Poor/uninsured, elderly/aged, or educationally disadvantaged

Research Design and Procedures

1. Overall Purpose

Describe the research questions or gap in knowledge the study proposes to address or contribute to in language that someone who is educated but not an expert in the field can understand.

* What is the overall purpose and aim of this project or study?

This is a single group study assessing the feasibility of hypertension management by community health workers (CHWs) equipped with a mobile clinical decision support (CDS) application and working with remote physician supervision.

2. Pre-Existing Information/Background Knowledge

* What prior information or knowledge exists to support the conduct of this project or study?

An estimated 1.13 billion people worldwide are currently living with hypertension, the leading preventable cause of death and disability.[1,2] Two thirds of these patients live in low- and middle-income countries (LMIC).[1,2] Treatment of hypertension has been found to be cost-effective in reducing morbidity and mortality across a broad range of settings.[3] Despite this, less than 10% of patients with hypertension in LMIC have good control of their blood pressure.[2] Health systems in LMIC, which are often focused on providing episodic care for acute illnesses and suffer from inadequate and poorly distributed health care infrastructure and workforce, are ill-equipped to address the rise in chronic non-communicable diseases (NCDs) such as hypertension.[4-6] Governments and NGOs are increasingly turning to community health workers (CHWs) - lay people trained to carry out a variety of tasks and who often are from or have a close connection to the communities they serve - to help fill care gaps for hypertension and other NCDs in LMIC.[7-10] In most cases, CHWs have played supportive (e.g. providing patient education) rather than direct care roles. While such programs have led to improved chronic disease outcomes, they still rely on clinic-based physicians, mid-level providers or nurses to directly provide medical management, and therefore do not address the essential problem of inadequate primary care infrastructure and workforce, particularly in rural areas. Overcoming this problem is key to reducing the growing burden of untreated hypertension in LMIC.

CHWs will meet with patients at enrollment visit and monthly thereafter. All study data will be collected using the CommCare application running on Android smartphones or tablets.

At enrollment, information on basic demographic information, past medical history, and current medications will be collected. CHWs will measure blood pressure, height and weight. Patients will also be administered the Hypertension Self-Care Activity Level Effects (H-Scale) questionnaire and the Patient Assessment of Chronic Illness Care (PACIC) survey on their satisfaction with their current hypertension treatment. They will be assessed for side effects of current medications and signs and symptoms of possible complications of hypertension, including ischemic heart disease, cerebrovascular disease, heart failure, and kidney disease. Blood will be drawn by venipuncture or capillary sample to assess lipid profile, serum creatinine, sodium, chloride, potassium, ALT and blood glucose.

Based on information entered by the CHWs into the CommCare application designed for this study, the application will provide recommendations (and underlying rationale for these recommendations) for prescription of antihypertensives (amlodipine and/or losartan OR enalapril) and medications to reduce cardiovascular risk (aspirin and atorvastatin) if indicated, lifestyle modification, and referral to the supervising physician ([name]) if indicated for potential complications of hypertension.

CHWs will then provide these interventions assisted by recommendations from the application. These procedures (aside from the enrollment panel of lab tests and questionnaires described above) will repeat at monthly visits.

CHWs will be able to contact [name], [name], or PI/PD [name] during the visit as needed for advice on patient management. After each visit, clinical data will be uploaded to CommCare's secure server and reviewed within one week of the visit by [name], [name], and/or [name], who will verify the current treatment plan and contact the coordinators of the CHW program if any changes to treatment are necessary, including the addition of other medications outside of the treatment algorithms per their clinical judgement. In the case that changes are necessary, CHWs will contact patients via phone or visit them at home to communicate and carry out changes.

CHWs will provide continuous feedback on the application, as well as program workflows and logistics. Based on this feedback, as well as monthly analysis of patient data, we will revise application algorithms, workflows, and user interface. This pragmatic design will allow for iterative application and program improvements, leading to a refined product that we can then scale up and evaluate in a larger controlled trial during the R33 phase of this NIH funded project.

At the 6 month visit, the blood tests and questionnaires listed above will be repeated and subjects will undergo semi-structured interviews to gain additional insight into their experience with the program.

4. Incidental or Adventitious Findings

* Will any study procedures produce incidental or adventitious findings (e.g., imaging scans, laboratory blood tests, depression screening questionnaires, etc.)?

Yes No

5. Instruments Involved

This question is intended to identify projects involving the development or use of medical devices. This does not apply to surveys, questionnaires, or statistical analysis software.

* Are there instruments of any kind, including software, tests run on samples, and algorithms, used in the study?

Yes No

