4.3 Statistical Design and Power

As this aim is focused on determining the feasibility of CHW-led hypertension management, power analyses were not performed. The main outcome of interest for this aim is the agreement of CHWs and physicians with the CDS application's recommendation for antihypertensive medications. Based on our experience with a similar diabetes program and published results of other CHW interventions, we have set an agreement threshold of 90%. In order to account for application updates during the early stages of the study, agreement will be assessed in the last 3 months of the feasibility study. Agreement will be summarized as the raw proportion of visits for which both the CHW conducting the visit and the physician reviewing post-visit data agreed with the antihypertensive recommendations provided by the application. As a secondary analysis, we will also calculate agreement individually for CHWs and the supervising physician to examine any discrepancies.

Other continuous outcomes will be summarized using means and standard deviations, both at baseline and 6 months after enrollment. Paired measures will be assessed for change using mean change and standard deviation of change. These changes will be assessed statistically versus a null hypothesis of no change using paired t-tests or Wilcoxon signed-rank tests on the paired differences. The continuous outcomes include systolic and diastolic blood pressure, CDS application usability score,⁶⁵ patient weight, LDL, HDL, total cholesterol, triglycerides, fasting glucose, Hypertension Self-care Activity Scale (H-SCALE) subscores,^{66,83} Patient Assessment of Chronic Illness Care (PACIC) subscale score and overall score,⁶⁴ and serum creatinine. Outcomes of study visit duration and physician review and care coordination time will be summarized over the whole length of the study, and examined for trends with respect to progression of the study, both with respect to calendar time, and time from patient enrollment.

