Other dichotomous outcomes will be summarized using proportions; time of assessment depends upon the outcome. For outcomes that are measured at baseline and 6 months after enrollment, the raw proportions will be reported for both periods, and association between the outcome and the two periods will be statistically assessed versus a null hypothesis of no association using McNemar's test. Outcomes to be assessed for change from baseline include systolic blood pressure \leq 140mmHg, systolic blood pressure \leq personalized goal, adherence to self-care activities as indicated by established H-SCALE cutoffs, and global patient satisfaction with hypertension care. Outcomes to be reported over the last 3 months of the trial include agreement of CHWs and physicians with various CDS application recommendations (atorvastatin and aspirin prescription, and referral recommendations). Outcomes to be reported throughout the whole trial include visit completion, medication adherence, incorrect CDS recommendations and application errors and malfunctions, complications of hypertension or hypertension treatment, and referral recommended by CHWs that are completed. For the outcomes assessed over the whole trial, or in the last three months, the raw proportions and occurrence counts will be reported for these periods. Additionally, instances of these outcomes / frequency of occurrence will also be examined versus calendar time, or time since subject enrollment, for potential trends. Patient retention will be determined by proportion of original patients that participated in a follow-up visit 6 months or longer from their initial visit.

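### Four safety analytes collected at enrolment and 6 months have no planned analysis, creatinine is summarised only at group level, and it is unstated whether a laboratory abnormality counts as a treatment complication

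*Protocol*

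**What the plan says.** **Collection.** Under Research Design and Procedures, item 3 (Study Procedures and Interventions), the protocol has blood taken at enrolment for a lipid profile, "serum creatinine, sodium, chloride, potassium, ALT and blood glucose". The panel is left out of the monthly cycle: "These procedures (aside from the enrollment panel of lab tests and questionnaires described above) will repeat at monthly visits". It comes back once: "At the 6 month visit, the blood tests and questionnaires listed above will be repeated". Each analyte therefore has two scheduled values per patient.

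**Treatment.** The same item has CHWs provide amlodipine and/or losartan or enalapril, plus aspirin and atorvastatin where indicated, on the application's recommendations.

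**Analysis.** SAP section 4.3 includes in its continuous outcomes "patient weight, LDL, HDL, total cholesterol, triglycerides, fasting glucose, Hypertension Self-care Activity Scale (H-SCALE) subscores" and, at the end of the same sentence, "and serum creatinine". These are summarised by mean and SD at baseline and at 6 months. Then: "Paired measures will be assessed for change using mean change and standard deviation of change", with a paired t-test or Wilcoxon signed-rank test against no change. The dichotomous outcomes tested for change are blood pressure targets, H-SCALE adherence and satisfaction. Over the whole trial the SAP also reports proportions and counts of "complications of hypertension or hypertension treatment", without defining them.

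**Clinical handling.** Protocol, Reporting Results, items 2.1 and 2.4: a supervising physician reviews laboratory tests monthly, abnormal findings are released to patients, and they are noted in the medical record.

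**The concern.** Potassium and creatinine are natural safety measures when losartan or enalapril is given, and ALT when a statin is given. The question for such values is how many patients moved out of range and how far. For potassium, sodium, chloride and ALT the supplied SAP plans nothing. For creatinine it plans summaries that average over patients, so one or two large changes can be diluted by the rest.

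The results are meant to feed a larger controlled trial of the same model (Protocol, Study Procedures and Interventions), so readers will look for a safety account. If the SAP is followed as written, that account would contain no count of patients whose safety laboratory values became abnormal, unless such cases happen to be included under the undefined complications item. Any laboratory table added later would be chosen after the data were seen.

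**Working it through.** The plan states no figure to reproduce: section 4.3 says no power analysis was done, and gives no laboratory threshold.

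**1. Item-by-item comparison.**

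| Panel item (Protocol) | Named in SAP 4.3? | Per-patient abnormality count? |
|---|---|---|
| Lipid profile | Yes (LDL, HDL, total cholesterol, triglycerides) | No |
| Glucose | Yes (fasting) | No |
| Creatinine | Yes | No |
| Sodium | No | No |
| Chloride | No | No |
| Potassium | No | No |
| ALT | No | No |

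Four of the seven named items have no analysis, and none of the seven has an abnormality count.

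**2. What a group-level test shows when few patients shift.** Input from the documents: n = 30 (Protocol, Subject Population, item 1). Assumed: 2 patients rise by 1.5 mmol/L in potassium, SD of change 0.4 among all others, no other shift, two-sided 5% test.

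- Movement of the mean: 2 × 1.5 / 30 = 0.10 mmol/L.
- Paired t-test, simulated with 40,000 runs: significant in about 9% (8.7%).
- Wilcoxon signed-rank test, same setting: about 7%.
- Range: with a rise of 1.0 or 1.5 mmol/L, an SD from 0.3 to 0.6, and 24 or 30 patients with both values, the t-test stays between about 7% and 9%.
- In SD units with n = 30: one patient shifted by 3 or 5 SDs gives 4.7% or 3.9%, no better than the 5% expected with no shift. Three such patients give 14.5% or 18%.

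A larger individual shift hardly helps the t-test, because the outlier inflates the SD as well as the mean.

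**3. What a count would show.**

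- 2 of 30 = 6.7%, exact 95% CI 0.8% to 22.1%.
- 0 of 30: two-sided 95% upper limit 1 − 0.025^(1/30) = 11.6%. With 24 completers (assumed), 1 − 0.025^(1/24) = 14.2%.
- Chance of at least one case among 30 at assumed true rates of 2%, 5% and 10%, from 1 − (1 − p)^30: 45%, 79% and 96%.

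**4. How many shifts arise with no harm.** Assume normally distributed values, a reference range covering the central 95%, and a correlation of 0.5 to 0.9 between the two draws. The probability of being inside at baseline and outside at 6 months is then 4.1% (correlation 0.5) to 2.0% (correlation 0.9).

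- Per analyte, 30 × 0.020 to 30 × 0.041 = 0.6 to 1.2 patients.
- Over five analytes (the four plus creatinine), about 3 to 6 shifts.
- Chance of two or more shifts on one analyte: 12% to 35%.

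One or two shifts on an analyte are therefore compatible with no effect at all.

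**The case against.** **A reader might infer that laboratory harm to an individual would go unseen.** The documents do not support that. Supervising physicians review laboratory results, abnormal findings are given to patients, and they are recorded (Protocol, Reporting Results, items 2.1 and 2.4). Data from each visit are also reviewed by a physician within a week. What is missing is a pre-specified summary across patients.

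**A reader might infer that laboratory values are reported as mean change only.** That is not right either. The SAP also gives the mean and SD at each time point, the SD of change, and a choice of paired tests. All of these remain group-level.

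**The complications outcome may already cover it.** It is counted over the whole trial and nothing excludes laboratory-detected events. This stands as far as it goes, but nothing includes them either, so two analysts could count differently.

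**This is a 30-patient, single-group feasibility pilot whose main outcome is agreement with the application.** True. No planned conclusion on agreement changes, the laboratory tests also serve patient care, and without a control group no shift can be attributed to CHW prescribing. That limits what the table can prove. It does not remove the reason to describe data already collected.

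**A simple count of patients inside the range at baseline and outside it at 6 months has its own faults.** It ignores direction and size, leaves out patients already abnormal at baseline, and picks up chance shifts (step 4 of the working). This stands, and the fix is shaped by it.

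**Only part of the SAP is available.** The absence is established for the section 4.3 text supplied, not for text removed before review.

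**Conclusion.** The point holds as a gap in pre-specified safety reporting. In the SAP text supplied, potassium, sodium, chloride and ALT have no planned analysis, creatinine has only group-level summaries, and the status of laboratory abnormalities within the complications outcome is not stated. Patient care is not in question.

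On size: four of seven panel items are unanalysed. Under the assumed scenario of two marked potassium rises among 30 patients, the planned type of paired t-test would be significant about 9% of the time (about 7% to 9% over the range tried), whereas a count reports 2 of 30 as it is. The shift sizes, SDs, 5% level and completer numbers are assumptions; the documents give only n = 30. The count has limits too: 2 of 30 is weak evidence of harm, and 0 of 30 does not exclude a rate of up to 11.6%. The change is worth making before analysis, as a descriptive addition.

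**What to change.** In SAP section 4.3:

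- Add potassium, sodium, chloride and ALT to the laboratory outcomes.
- For these four and creatinine, report a baseline-by-6-month shift table against the laboratory's reference range (below, within, above), so that shifts in each direction are shown separately, with counts, proportions and exact 95% confidence intervals. State the number of patients with both values.
- Add a listing of individual values that shows the size of each change and includes patients already outside the range at baseline.
- State whether a laboratory abnormality counts toward the complications outcome and, if so, by what criterion, set by the study team before analysis.
- Label the table as descriptive: no attribution to CHW prescribing, chance shifts expected, and the upper limit quoted where no patient shifts.

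The planned means and tests for creatinine can stay alongside. The cost is one small table and a listing from data already collected, with no new blood draw and no change in sample size. The downside is a little extra analysis and some chance shifts that will need explaining.
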